Baseline measures for Groups 1 and 2 will include laboratory assessments for HBV DNA, HBV serology, HCV, HDV, and HIV polymerase chain reaction (PCR) testing, HBV genotyping, serum renal and bone chemistries, liver function, hematology, urinalysis. Dual Energy X-ray Absorptiometry (DEXA) imaging and a physical exam, including current concomitant medications (including dietary supplements) and any renal or bone AEs, will also be collected.

FREQUENCY OF STUDY PROCEDURES ([Appendix 2](#)):

Subjects enrolled to either Group 1 or 2 will have the following measures assessed:

- HBV DNA: every 12 weeks from Baseline to Week 96
- HBV serology: every 24 weeks from Baseline to Week 96
- Liver chemistry (i.e., alanine aminotransferase (ALT), alkaline phosphatase (ALP), aspartate aminotransferase (AST), total and direct bilirubin, total protein, albumin, gamma glutamyl transpeptidase (GGT), lactate dehydrogenase (LDH), creatine kinase (CK): every 24 weeks from Baseline to Week 96
- Hematology (i.e., complete blood count with differential and platelets, PT/INR): every 24 weeks from Baseline to Week 96
- Physical Examination and Drug Dispensing: every 12 weeks from Baseline to Week 96

Subjects enrolled to Group 1 will have the following additional monitoring:

- DEXA: every 24 weeks from Baseline to Week 96 (5 scans)
- Serum bone chemistry (i.e., calcium, phosphorus, vitamin D levels (25-hydroxy and 1,25 dihydroxyvitamin), parathyroid hormone (PTH), osteocalcin, bone-specific alkaline phosphatase, N and C telopeptides): every 24 weeks from Baseline to Week 96
- Serum renal chemistry (i.e., glucose, creatinine, calculated creatinine clearance, magnesium, bicarbonate, chloride, potassium, sodium): at 4 weeks and 12 weeks from Baseline and every 12 weeks thereafter to Week 96, according to SmPC

- Urinalysis (i.e., protein, glucose, creatinine, phosphate, bicarbonate, blood, calcium): at 4 weeks and 12 weeks from Baseline and every 12 weeks thereafter to Week 96

Subjects enrolled to Group 2 will have the following monitoring:

- DEXA: every 48 weeks from Baseline to Week 96 (3 scans)
- Serum bone chemistry (i.e., calcium, phosphorus, vitamin D levels (25-hydroxy and 1,25 dihydroxyvitamin), PTH, osteocalcin, bone-specific alkaline phosphatase, N and C telopeptides): every 48 weeks from Baseline to Week 96
- Serum renal chemistry and urinalysis according local standards of care

Product, Dose, and
Mode of
Administration:

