300mg oral Tenofovir disoproxil fumarate (Tenofovir DF), which is equivalent to 245mg Tenofovir disoproxil, following enhanced patient monitoring protocol for bone and renal biomarkers

Reference Therapy,
Dose, and Mode of
Administration:

300mg oral Tenofovir DF following local standards of care for patient monitoring for renal biomarkers

Criteria for Evaluation:

Safety:

The primary safety endpoint is the indication of a cumulative incidence of a $\geq 4\%$ decrease from Baseline BMD of the spine or whole body through Week 96. Secondary endpoints include bone and renal AEs. Bone AEs may include reports of bone pain or fractures. Renal AEs may include reductions in creatinine clearance, and clinical and laboratory evidence of Grade 3 or greater renal tubulopathy or toxicity (e.g. proximal renal tubulopathy, Fanconi syndrome).

Bone and renal AEs, concomitant medications (including dietary supplements) and specified clinical laboratory tests will be collected each time subjects from Group 1 or Group 2 return for scheduled monitoring by the study site over a 96 week period.

Efficacy:

An efficacy analysis will be conducted after the last assigned subject reaches Week 96. The analysis will evaluate the difference in the proportion of subjects (Group 1 and 2 data will be pooled, as subjects have exposure to a single mode of therapy) achieving a composite endpoint of HBV DNA < 400 copies/mL and ALT normal at Week 96.

Pharmacokinetics: Not applicable

Statistical Methods:

The primary safety analysis will be performed after the last subject reaches Week 96 on Tenofovir DF treatment among both monitoring groups. The primary analysis will evaluate quantitative reductions in spine or whole body BMD compared to baseline assessments through DEXA scanning. A key secondary study objective is to assess within-group and between-group differences in renal biomarker changes (e.g., creatinine clearance using the Schwartz formula, glucosuria, proteinuria) suggestive of renal toxicity. To evaluate the time to detection of renal or bone AEs among the assigned monitoring groups, estimations of incidence rates (events over person time on Tenofovir DF) and time to event analysis will be determined. The evaluation of other clinically relevant endpoints such as sustained virologic response, serologic status, and development of Tenofovir DF resistance will also be assessed as secondary study outcomes for each monitoring group and as a combined cohort.

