3.2. Study Design

The study will be a prospective cohort comprised of HBV infected adolescents who initiate Tenofovir DF therapy in clinics across Europe. The subjects will be assigned to one of two monitoring groups using a validated computer-generated tool for randomization. Subjects will be assigned to Group 1 or 2 upon enrollment into the study but prior to Baseline laboratory and DEXA imaging assessments.

DEXA scans are non-invasive tests to measure bone mineral density as well as skeletal maturity and bone mass. DEXA scans emit an average effective dose of 0.001 milli Sieverts (mSv) in adults {22238}. These scans emit very minor radiation (i.e., in comparison, one mammogram has an effective dose of 0.4 mSv), and with such low doses of radiation do not pose concerning health hazards. Data are based on adult studies and may have a higher relative effective dose, particularly in very young children. Repeated DEXA scans should be conducted using the same model of equipment, if possible, and scans should be read in a standardized manner.

Group 1 will receive Tenofovir DF for the treatment of CHB infection, followed over 96 weeks using an enhanced monitoring protocol which includes more frequent laboratory bone biomarker testing and lumbar spine and whole-body DEXA scans than specified for Group 2. With the exception of an enhanced monitoring protocol for bone and renal outcomes, subjects will be managed according to local standards of care.

Group 2 will be the comparator group of subjects receiving Tenofovir DF for the treatment of CHB infection and with the exception of pre-specified bone monitoring, managed according to local standards of care. Group 2 will receive bone biomarker testing, lumbar spine and whole-body DEXA at Baseline, Weeks 48 and 96.

Both groups will be monitored for 96 weeks on Tenofovir DF during clinic visits for response to treatment, AEs, adherence to supplementary vitamins and mineral intake assessments.

Both groups will be required to have DEXA (whole body and spine) scans for BMD at Baseline (week 0) and prior to receipt of Tenofovir DF, and at the end of the study period (Week 96). Group 2 will be a comparator cohort to Group 1 in evaluating the hypothesis of whether enhanced monitoring for renal and BMD changes and AEs provides a net benefit in preventing renal- or bone-related adverse outcomes to adolescents receiving Tenofovir DF therapy for HBV.

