Screening measures for Monitoring Groups 1 and 2 will include determining a subject's eligibility into the study with the following criteria: current age, documentation of chronic HBV infection, prior Tenofovir DF exposure, weight, laboratory assessments, ability to swallow solid tablets, subject's ability to adhere to treatment regimen, obtaining written informed consent from subject's parent or legal guardian or obtain informed assent from the subject

Baseline measures for Monitoring Groups 1 and 2 will include laboratory assessments for HBV DNA, HBV serology, HCV, HDV, and HIV polymerase chain reaction (PCR) testing, HBV genotyping, serum renal and bone chemistries, liver function, hematology, urinalysis. DEXA imaging, a physical exam (including pregnancy testing for females), current concomitant medications and any reported prior bone and renal AEs, will also be collected.

FREQUENCY OF STUDY PROCEDURES ([Appendix 2](#)):

Subjects enrolled to either Group 1 or 2 will have the following measures assessed:

- HBV DNA: every 12 weeks
- HBV serology: every 24 weeks
- Liver chemistry (i.e., alanine aminotransferase (ALT), alkaline phosphatase (ALP), aspartate aminotransferase (AST), total and direct bilirubin, total protein, albumin, gamma glutamyl transpeptidase (GGT), lactate dehydrogenase (LDH), creatine kinase (CK) every 24 weeks
- Hematology (i.e., complete blood count with differential and platelets, PT/INR): every 24 weeks
- Physical Examination and Drug Dispensing: every 12 weeks
- Documentation of bone or renal AEs since the subject's last visit
- Documentation of medical management in the event of bone or renal AEs

Subjects enrolled to Group 1 will have the following additional monitoring;

- DEXA: every 24 weeks from Baseline to Week 96 (5 scans)
- Serum bone chemistry (i.e., calcium, phosphorus, vitamin D levels (25-hydroxy and 1, 25 dihydroxyvitamin), parathyroid hormone (PTH), osteocalcin, bone-specific alkaline phosphatase, N and C telopeptides): every 24 weeks
- Serum renal chemistry (i.e., glucose, creatinine, calculated creatinine clearance, magnesium, bicarbonate, chloride, potassium, sodium): at 4 weeks and 12 weeks from Baseline and every 12 weeks thereafter, according to SmPC
- Urinalysis (i.e., protein, glucose, creatinine, phosphate, bicarbonate, blood, calcium): at 4 weeks and 12 weeks from Baseline and every 12 weeks thereafter

Subjects enrolled to Group 2 will have the following monitoring:

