3.3. Study Treatments

The proposed study is an open-label trial of 300mg oral Tenofovir DF which is equivalent to 245mg Tenofovir disoproxil, taken once daily. Tenofovir DF is packaged in white, high-density polyethylene (HDPE) bottles with a white child resistant cap. There are 30 tablets per bottle. Each bottle also contains silica gel as a desiccant to protect the product from humidity and fiber packing to protect the product during handling and shipping.

During Weeks 0 to 96, subjects will be provided with sufficient supplies for 12 weeks of dosing. At a minimum, each bottle will be labeled with a lot number, the protocol number, administration instructions, storage instructions, expiration date, Sponsor name and address. Additional information will be included according to the requirements of the protocol and local law.

Tenofovir DF will be supplied by Gilead as per its current commercial tablet formulation for the EU (300mg Tenofovir DF) for patients greater than 35 kg. There will be no difference in

medication formulation or frequency as per Tenofovir DF SmPC among subjects assigned to either Group 1 or Group 2.

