6.4.2. Group 1: Week 12 and 36 Assessments

Study Visit for Weeks 12 and 36 should be completed \pm 7 days of the protocol-specified visit date, based on the Baseline Visit. Group 2 subjects will follow local standard of care for renal monitoring and AE collection. The following assessments and procedures will be performed and recorded on CRFs:

- Complete physical examination including, vital signs, body weight and height
- Group 1: Urinalysis (protein, glucose, creatinine, phosphate, bicarbonate, blood, calcium), fasting required
- Blood samples for:
 - Group 1: Serum renal chemistry (creatinine, glucose, creatinine clearance (calculated), magnesium, bicarbonate, chloride, potassium, sodium), fasting required
 - Plasma HBV DNA (PCR method)
- Review of bone and renal AEs and any associated medical management
- Concomitant medications (including dietary supplements such as calcium, vitamin D, phosphorus)
- Assessment of medication adherence
- Tenofovir DF dispensing and instructions on appropriate dosing and administration

- Screening for pregnancy (urine screen)

Subjects who discontinue the study prior to the Week 12 or 36 Visit will complete all Week 12 or 36 assessments and procedures at an Early Drug Discontinuation Visit, to be completed within 72 hours of last dose of Tenofovir DF. Subjects who have received at least one dose of Tenofovir DF and permanently discontinue treatment will be followed for 24 weeks off treatment or up to initiation of an alternative treatment regimen, whichever occurs first.

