6.4.3. Groups 1 and 2: Week 24 and 72 Assessments

Study Visit for Weeks 24 and 72 should be completed \pm 7 days of the protocol-specified visit date, based on the Baseline Visit. Group 2 subjects will follow local standard of care for renal monitoring. The following assessments and procedures will be performed and recorded on CRFs:

- Complete physical exam including vital signs, body weight and height
- Blood samples for:
 - Plasma HBV DNA (for PCR)
 - HBV serology (HBeAg and HBsAg; anti-HBe and anti-HBs (if HBsAg negative))
 - Hematology (CBC with differential and platelets, PT/INR)
 - Group 1: Serum renal chemistry (glucose, creatinine, creatinine clearance (calculated), magnesium, bicarbonate, chloride, potassium, sodium), fasting required
 - Liver chemistry (ALT, ALP, AST, total and direct bilirubin, total protein, albumin, GGT, LDH, CK), fasting required
 - Group 1 Only: Serum bone chemistry (calcium, phosphorus, 1,25 hydroxy vitamin D, PTH, osteocalcin, bone alkaline phosphatase, N and C telopeptides), fasting required
- Group 1 Only: DEXA (+/- 14 days of the Week 24 or Week 72 visit) scan of spine and whole body
- Group 1: Urinalysis (glucose, protein, creatinine, phosphate, bicarbonate, blood, calcium), fasting required
- Review of bone and renal AEs and any associated medical management
- Concomitant medications (including dietary supplements such as calcium, vitamin D, phosphorus)
- Assessment of medication adherence

- Tenofovir DF dispensing and instructions on appropriate dosing and administration
- Screening for pregnancy (urine screen)

Subjects who discontinue the study prior to the Week 24 or 72 Visit will complete all Week 24 or 72 assessments and procedures at an Early Drug Discontinuation Visit, to be completed within 72 hours of last dose of Tenofovir DF. Subjects who have received at least one dose of Tenofovir DF and permanently discontinue treatment will be followed for 24 weeks off treatment or up to initiation of an alternative treatment regimen, whichever occurs first.

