6.4.5. Groups 1 and 2: Week 60 and 84 Assessments

Study Visit for Weeks 60 and 84 should be completed \pm 7 days of the protocol-specified visit date, based on the Baseline Visit. Group 2 subjects will follow local standard of care for renal monitoring. The following assessments and procedures will be performed and recorded on CRFs:

- Complete physical exam including vital signs, body weight and height
- Blood samples for:
 - Plasma HBV DNA (for PCR)
 - Group 1: Serum renal chemistry (glucose, creatinine, creatinine clearance (calculated), magnesium, bicarbonate, chloride, potassium, sodium), fasting required
- Group 1: Urinalysis (glucose, protein, creatinine, phosphate, bicarbonate, blood, calcium), fasting required
- Review of bone and renal AEs and any associated medical management
- Concomitant medications (including dietary supplements such as calcium, vitamin D, phosphorus)
- Assessment of medication adherence
- Tenofovir DF dispensing and instructions on appropriate dosing and administration
- Screening for pregnancy (urine screen)

Subjects who discontinue the study prior to the Week 60 or 84 Visit will complete all Week 60 or 84 assessments and procedures at an Early Drug Discontinuation Visit, to be completed within 72 hours of last dose of Tenofovir DF. Subjects who have received at least one dose of

Tenofovir DF and permanently discontinue treatment will be followed for 24 weeks off treatment or up to initiation of active treatment, whichever occurs first.

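### Protocol 6.4.2 contradicts itself and the synopsis on whether Group 2 has adverse event review at Weeks 12 and 36

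*Protocol*

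**What the plan says.** **Section 6.4.2 (Weeks 12 and 36).** The heading names Group 1 only, and the text says "Group 2 subjects will follow local standard of care for renal monitoring and AE collection". The procedure list that follows contains a review of bone and renal AEs and their management, with no group label. In that list only urinalysis and serum renal chemistry are labelled Group 1.

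**Synopsis, Criteria for Evaluation.** Bone and renal AEs "will be collected each time subjects from Group 1 or Group 2 return for scheduled monitoring by the study site".

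**Section 3.2.** "Both groups will be monitored for 96 weeks on Tenofovir DF during clinic visits for response to treatment, AEs". The list of measures for either group includes "Documentation of bone or renal AEs since the" last visit.

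**Group 2 attendance at Weeks 12 and 36.** The synopsis list for both groups has "Physical Examination and Drug Dispensing: every 12 weeks from Baseline to Week 96", and HBV DNA at the same interval. Section 3.3 says "subjects will be provided with sufficient supplies for 12 weeks of dosing". SAP Appendix 1 labels the examination row for both groups and marks it at Weeks 12 and 36.

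**Parallel sections.** For Weeks 24 and 72, 6.4.3 says "Group 2 subjects will follow local standard of care for renal monitoring" and stops there. Sections 6.4.4 and 6.4.5 use the same wording, and 6.4.5 is headed "Groups 1 and 2: Week 60 and 84 Assessments".

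**Appendix 2.** The AE assessment row is marked at Weeks 12 and 36. Its dagger footnote says that Group 2 may have new AEs assessed on return for renal monitoring, under standard of care and within the 12-week examination intervals.

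**The concern.** The two groups receive the same drug and differ by design in how often they are tested. Detection is part of what the study examines. Section 8.6 compares recorded renal or bone AEs between the groups, 8.1.3 has a secondary endpoint built on exposure time when such AEs are detected, and the hypothesis in 8.9 concerns their timing, management and outcomes.

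If sites ask Group 1 about AEs at Weeks 12 and 36 but leave Group 2 to local habit, events in Group 2 could be found later, or some might not be recorded, for a reason unrelated to the testing schedules under comparison. Both visits fall before Week 48, the point at which 8.2.1.2 planned an interim analysis of renal and bone AEs. They also fall in the period for which most data exist, since SAP 2.1 reports that only two patients completed 96 weeks.

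**Working it through.** **Text comparison.** The plan states no figure on this point, so there is none to reproduce.

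| Place | Group 2 AE review at Weeks 12 and 36 |
|---|---|
| Synopsis | Required at each scheduled return |
| 3.2, both-groups statements | Required at clinic visits; no interval given |
| 6.4.2 heading and sentence | Left to local care |
| 6.4.2 procedure list | Included, no group label |
| Appendix 2 row | Marked |
| Appendix 2 dagger | May be assessed |

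The sentence in 6.4.2 is word for word the one in 6.4.1, which covers the Week 4 visit of Group 1 alone. That suggests it was carried over. The Group 1 labels on two items of the 6.4.2 list would serve no purpose unless the section covered both groups.

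**Scheduled on-treatment reviews.**
- Group 1: Weeks 4, 12, 24, 36, 48, 60, 72, 84, 96, which is 9.
- Group 2 if the sentence is followed: Weeks 24, 48, 60, 72, 84, 96, which is 6.
- Group 2 if the list is followed, or after the fix: Weeks 12, 24, 36, 48, 60, 72, 84, 96, which is 8.
- Through Week 48 the counts are 5, 2 and 4. Adding the 30-day follow-up to the 96-week counts gives 10, 7 and 9.

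**Mean wait from onset to next scheduled review.** With onset uniform over T weeks and reviews separated by intervals L, the mean wait is ΣL²/(2T). Uniform onset is an assumption; the documents give no onset pattern.

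| | T = 48 | T = 96 |
|---|---|---|
| Group 1 | (4² + 8² + 3×12²)/96 = 512/96 = 5.3 | (4² + 8² + 7×12²)/192 = 1088/192 = 5.7 |
| Group 2, sentence followed | (2×24²)/96 = 1152/96 = 12.0 | (2×24² + 4×12²)/192 = 1728/192 = 9.0 |
| Group 2, list followed or after fix | (4×12²)/96 = 576/96 = 6.0 | (8×12²)/192 = 1152/192 = 6.0 |

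Check: only onsets in Weeks 0–12 and 24–36 are affected, and each is delayed by 12 weeks. Over 96 weeks that is 24/96 × 12 = 3.0 = 9.0 − 6.0. Through Week 48 it is 24/48 × 12 = 6.0 = 12.0 − 6.0.

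**Range.** The 12.0 and 9.0 assume that Group 2 has no contact other than the scheduled reviews, so they are upper bounds. The asterisk footnote in Appendix 2 allows local renal monitoring to follow the SmPC intervals, which the synopsis gives for Group 1 as Weeks 4 and 12 and then 12-weekly. If Group 2 is seen on that schedule and AEs are assessed there, its wait equals that of Group 1: 5.3 and 5.7 weeks. The longest gap between Group 2 reviews is 24 weeks in the worst case and 12 if the list is followed.

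**The case against.** The strongest reply is that the plan already contains the review. The AE item in the 6.4.2 list has no group label, and Appendix 2 marks AE assessment at both weeks. A site working from the list or the table would do it. The dagger can be read as additive, allowing further assessment at local renal visits between the 12-weekly ones. If it is instead read as making review optional, it does so for every Group 2 visit, since it applies to the whole row, and the count of 6 would then be wrong too.

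Other points also carry weight:
- Only the synopsis says each time. Section 3.2 speaks of clinic visits, and its AE item has no interval. That item reaches back to the last visit, so a missed review can be made good at the next.
- Section 7.3 requires all bone and renal AEs in every subject, and 8.6.2 summarises events by onset date. A late report therefore keeps its onset.
- Section 3.2 does say that Group 2, apart from bone monitoring, is managed to local standards, and that Group 1 has more frequent clinical assessments. The sentence could be deliberate.

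The first two of these points limit the effect but do not remove the conflict. On the third, a deliberate choice would contradict the synopsis and would leave Weeks 12 and 36 treated differently from Weeks 60 and 84 without a stated reason. Section 8.9 describes the groups as differing in how often tests are done, which is separate from whether AEs are asked about.

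A reader might infer that Group 2 had no AE review at these weeks, or that by-group AE counts are biased. The documents do not support either. They show conflicting instructions and say nothing of what sites did. They give no capture fraction from which a bias in counts could be computed.

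**Conclusion.** The inconsistency is real, both inside 6.4.2 and between it and the synopsis, the both-groups statements in 3.2 and sections 6.4.3 to 6.4.5. The dagger footnote leaves it unresolved. The consequence is possible, not certain: a site that took the sentence over the list could omit active review in Group 2 at Weeks 12 and 36, so that detection would be later there.

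The size runs from nil to the upper bounds worked out above, a 3.0-week longer mean wait in Group 2 over 96 weeks and 6.0 weeks longer through Week 48. These rest on uniform onset and no other contact. BMD is unaffected, because the scan schedule does not depend on AE review. SAP 1.4 and 2.1 report 30 subjects enrolled and make the final analysis descriptive by group and pooled. No table listed in SAP Appendix 3 has a title naming time to detection, but section 7.1.7 on additional AE analyses is blacked out, so that cannot be settled. Severity is minor.

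**What to change.** In the protocol text:
- Head 6.4.2 for Groups 1 and 2, as 6.4.3 to 6.4.5 are, and keep the Group 1 labels on urinalysis and renal chemistry.
- Delete the words on AE collection from its Group 2 sentence, so that only renal monitoring is left to local care. Leave the Week 4 section as it is.
- Reword the Appendix 2 dagger footnote so that bone and renal AE review is required in Group 2 at each 12-weekly visit, with any assessment at local renal visits additional.

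The cost is one heading, one phrase and one footnote. No visit is added, and the planned differences in DEXA, bone, renal and urine testing do not change.

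As the study has closed, the practical step is in the report. It should state how AE review was done in Group 2 at Weeks 12 and 36, and caution the reader on by-group AE counts and detection times. SAP 3.9.1 describes Group 2 visits and tests as ad hoc. That remark concerns efficacy data, but it makes the question worth answering.
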